8.4.6 Pregnancy and assessments of fertility

Serum pregnancy tests will be conducted for all women of childbearing potential at Screening, annually and EOS visits. Urine pregnancy tests will be conducted for all women who are of child bearing potential at all other planned clinic visits as indicated in Table 8-1 and Table 8-2 prior to study drug administration. In addition, the subjects will be provided with urinary pregnancy test kits for monthly home pregnancy testing required between the scheduled clinic visits prior to study drug administration. The subjects will document the date and result of each home pregnancy test. In case of a positive test result, the subject must contact the Investigator immediately for confirmatory testing at the Investigator's discretion.

In addition, the Investigator will review the contraception status with the subject at each visit to ascertain that the subject continues to comply with protocol requirements for highly effective contraception as applicable.

All pre-menopausal women who are not surgically sterile will have pregnancy testing. A woman is considered of childbearing potential from menarche and until becoming post-menopausal unless permanently sterile. Permanent sterilization methods include hysterectomy, bilateral salpingectomy and bilateral oophorectomy. Medical documentation of oophorectomy, hysterectomy, or tubal ligation must be retained as source documents.

A postmenopausal state is defined as no menses for 12 months without an alternative medical cause and an appropriate clinical profile.

In absence of a medical documentation confirming permanent sterilization, or if the post-menopausal status is not clear, the investigator should use his medical judgment to appropriately evaluate the fertility state of the woman and document it in the source document. Additional pregnancy testing might be performed if required by local requirements.

As per Section 4.6, during a public health emergency as declared by local or regional authorities' i.e. pandemic, epidemic or natural disaster, that limits or prevents on-site study visits, if subjects cannot visit the site to have serum pregnancy tests, urine pregnancy test kits may be used. Relevant subjects can perform the urine pregnancy test at home and report the result to the site.

It is important that subjects are instructed to perform the urine pregnancy test first and only if the test result is negative proceed with the administration of the study treatment. A communication process should be established with the subject so that the site is informed and can verify the pregnancy test results (e.g. following country specific measures).

8.4.7 Appropriateness of safety measurements

The safety assessments included in this study (Table 8-1 and Table 8-2) are standard for the MS indication and study subject population and appropriate based on the current safety profile of ofatumumab as seen in both Phase 2 and Phase 3 studies, see Investigator's Brochure (IB) for more information.

The use of C-SSRS to detect suicidal ideation behavior is currently mandated in studies of CNS active drugs, for further details, refer to Section 10.2.1.

8.5 Additional assessments

8.5.1 Clinical Outcome Assessments (COAs)

Patient reported / patient centric outcome (PRO) measures are included in this study to provide an empirical assessment from the subject's perspective of the benefits of treatment that cannot be gained from MRI, EDSS, or relapse measurement. These PROs will be completed according to the schedule in Table 8-1. The CCI , CCI and CCI will be collected electronically in a handheld CCI. The subject must be given the handheld to be completed at the scheduled visit before any clinical assessments are completed. In the event the questionnaires are unavailable for the subject during a visit (e.g. technical issue with the handheld), there is a web backup option available for the subject to complete. Paper versions for CCI , CCI and CCI are not available for this study.

8.5.1.1 CCI

The CC version 2 (Hobart and Cano 2009) will be used to assess health-related quality of life and will be evaluated at planned visits according to Table 8-1 when Patient Reported Outcomes (PROs) are planned. CC is a CC , self-administered questionnaire that includes two domains, physical and psychological. Responses are captured on a 4-point scale ranging from "not at all" (1) to "extremely" (4), where higher scores reflect greater impact on day-to-day life.

It is a clinically useful and scientifically sound measure of the impact of MS from the subject's perspective suitable for clinical trials and epidemiological studies (Hobart et al 2001). It is considered a reliable, valid and responsive PRO measure that complements other indicators of disease activity used to improve the understanding of the impact of MS.

The questions in the scale ask the subject for their views about the impact of MS on their day-to-day life during the past 2 weeks. The **CCI** takes approximately 5 minutes to complete, and will be translated into the appropriate language of the subject.

8.5.1.2 **CCI**

The **CC** will be used to psychometrically evaluate the patients' satisfaction with ofatumumab treatment and will be recorded at planned visits according to Table 8-1 when Patient Reported Outcomes (PROs) are planned. The **CCI** is a sound and valid measure of the major dimensions of patients' satisfaction with medication and a good predictor of adherence across different types of medication and patient population.

The Version 1.4 comprises 14 items across four domains focusing on effectiveness (3 items), side effects (5 items), convenience (3 items), and global satisfaction (3 items) of the medication over the previous 2–3 weeks, or since the subject's last use. With the exception of item 4 (presence of side effects; yes or no), all items have 5 or 7 responses, scored from 1 (least satisfied) to 5 or 7 (most satisfied). The 7-item scales had a non-neutral midpoint, such that there were more positive response options than negative response options, to allow precise information to be obtained at the upper end of the score distribution. Item scores are summarized to give four domain scores, which are in turn transformed to a scale of 0–100. For the purpose of the study, medication side effects will be only captured via the AE reporting form to avoid inconsistency in data capture.

8.5.1.3 **CCI**

Fatigue in the context of multiple sclerosis (MS) is a complex symptom with still unknown pathophysiology. The CCI is a 20 item scale developed as a measure of cognitive and motor fatigue for people with MS. CCI will be assessed at planned visits according to Table 8-1 when Patient Reported Outcomes (PROs) are planned. Sensitivity and specificity scores allow reliable assessment and the statistically identified cutoff values provide detailed quantification of fatigue in clinical routine. The tool has been extensively validated in different languages, and practice settings. Improving fatigue in patients with MS is difficult and drug trials have shown mixed results. Given the high impact on employment and quality of life, the scale will be utilized.

[figure not shown]
8.5.1.4 **CCI**

Depression and anxiety are reported to have a severe negative impact on people with MS and are associated with a reduction in health related quality of life.

is a 14-item self-reported measure with two subscales. A score of 8 or above on either subscale indicates possible clinically relevant anxiety or depression. During the study, if the subjects scores 8 or above, the investigator should use the clinical judgment if the subject need additional treatment and document this in the CRF.

The **CCI** has been found to have high sensitivity and specificity in relation to clinical interview and to other mood rating scales in people with MS. The scale is administered and data captured electronically taking approximately 8 minutes to complete.

8.5.1.5

8.5.2 Biomarkers

Blood samples will be drawn for analysis of exploratory biomarkers according to the schedule in Table 8-1 and Table 8-2. These specimens will be used to identify and/or verify potential markers that may be predictive of disease activity, disease course and/or clinical response to treatment. Analysis of these specimens will include NfL and CCI (for both, also refer to Section 8.3.3). Samples for biomarker assessment should be taken prior to dosing at Visit 1. For any later biomarker visits, if the visit coincides with the day of the monthly injection, the subject should not take the injection in the morning before coming to the site so that the biomarker sample can be drawn prior to administration. The biomarker sample collection date and time must be entered on the appropriate eCRF.

Page 71

The details describing the collection, handling, storage and shipment requirements of samples will be provided in the laboratory manual.

9 Study discontinuation and completion

9.1 **Discontinuation**

9.1.1 Discontinuation of study treatment

Discontinuation of study drug for a subject occurs when study drug is stopped earlier than the protocol planned duration, and can be initiated by either the subject or the investigator.

The investigator must discontinue study treatment for a given subject if he/she believes that continuation would negatively affect the subject's well-being.

Study drug must be discontinued under the following circumstances:

- Subject/guardian decision (Section 9.1.2)
- Pregnancy (Section 8.4.6 and Section 10.1.6)
- Use of prohibited treatment (Section 6.2.2)
- Diagnosis of PML •
- Subjects with active serious infections or reactivation (e.g. tuberculosis, hepatitis B or C)
- Skin and/or mucosal reactions which raise the suspicion of severe generalized major skin reactions (Stevens-Johnson syndrome, or toxic epidermal necrolysis-Lyell's syndrome)
- Hypersensitivity to the study medication
- Any situation in which study participation might result in a safety risk to the subject
- Protocol violation that results in a significant risk to the subject's safety
- Emergence of certain adverse events, such as malignancy (except successfully treated basal cell carcinoma, in situ squamous cell carcinoma and in situ carcinoma of cervix of uterus), liver failure or serious chronic infection (such as human immunodeficiency virus (HIV))
- Severe hypoproteinemia
- Interstitial lung disease or new onset or worsening of pulmonary symptoms, such as persistent cough and dyspnea, with or without associated fever, suspicious of interstitial lung disease
- Non-compliance with study drug or study procedures

Study treatment discontinuation should be considered under the following circumstances:

- For subjects who meet the criterion for 6mCDW on EDSS during the study, the investigator must reassess the benefits and risks of continuing study treatment. The investigator will also discuss the further treatment with the subject, including any other MS treatment options that may be available to the subject. The outcome of the discussion with the subject must be documented in the subject's source information
- In case the investigator deems the benefit-risk of continuing study treatment to be unfavorable or if the subject does not wish to continue study treatment, the subject will be discontinued from the study and will enter the Safety Follow-up period (Table 8-2). The investigator will be notified by the Sponsor when a subject meets the criterion for 6mCDW.

If discontinuation of study drug occurs, the investigator should make a reasonable effort to understand the primary reason for the subject's premature discontinuation of study drug and record this information.

Subjects who discontinue study drug or who decide they do not wish to participate in the study further should NOT be considered withdrawn from the study UNLESS they withdraw their consent (see Section 9.1.2). Subjects that discontinue treatment should complete the EOS visit and move to the Safety Follow-up as per Table 8-2. If they fail to return for these assessments for unknown reasons, every effort (e.g. telephone, e-mail, letter) should be made to contact the subject/pre-designated contact as specified in Section 9.1.3. This contact should preferably be done according to the study visit schedule.

If the subject cannot or is unwilling to attend any visit(s), the site staff should maintain regular contact with the subject, or with a person pre-designated by the subject. This contact should preferably be done according to the study visit schedule for up to 6 months post last study drug administration.

After study drug discontinuation, at a minimum, in abbreviated visits, the following data should be collected at clinic visits or via telephone/email contact:

- New / concomitant treatments
- Adverse Events / Serious Adverse Events

The investigator must also contact the IRT to register the subject's discontinuation from study drug.

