	Subject transitioning from either any fumarate-based RMS approved therapies, such as dimethyl fumarate (DMF) or diroximel fumarate (DRF), or fingolimod which was administered for a period of at least 6 months, as their last DMT before first study drug administration
	Breakthrough disease activity while the participant was adequately using fumarates or fingolimod prior to transitioning for a minimum of 6 months as evidenced by one or more clinically reported relapses or one or more signs of Magnetic Resonance Imaging (MRI) activity (e.g. Gd+ enhancement, new or enlarging T2 lesions)
	Neurologically stable within one month prior to first study drug administration
Key Exclusion criteria	Subjects with primary progressive MS (Polman et al 2011) or SPMS without disease activity (Lublin et al 2014)
	Subjects meeting criteria for neuromyelitis optica (Wingerchuk et al 2015)
	Disease duration of more than 10 years since diagnosis
	Pregnant or nursing (lactating) women
	Women of child-bearing potential unless they are using highly effective forms of contraception during dosing and for at least 6 months after stopping study medication.

Electrocardiogram (ECG)

Page 25

Protocol No. COMB157G23101

Other assessments	 Patient reported outcomes (PROs) CCI CCI CCI CCI CCI
Data analysis	All efficacy data will be analyzed according to the intent-to-treat principle. The primary analysis for the ARR is estimated based on the FAS using individual relapse count as the response variable with time in study as an offset variable. Secondary analysis includes AE safety related endpoints. Exploratory endpoints will be presented descriptively.
Key words	Interventional, transitioning, clinical trial, effectiveness, safety, open-label, ofatumumab, relapsing multiple sclerosis, treatment satisfaction, patient reported outcomes

1 Introduction

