1.2 Purpose

The purpose of the study is to complement the ofatumumab Phase 3 program by exploring outcomes of patients transitioning from any fumarate-based RMS approved therapy, such as dimethyl fumarate (DMF generic or branded) or diroximel fumarate (DRF), or fingolimod (generic or branded) to ofatumumab due to breakthrough disease in a specialized clinical practice and tertiary care settings.

Breakthrough disease has been defined as:

- At least one documented relapse during previous year OR two relapses during previous two years prior to inclusion
- Or presence of at least one Gd+ lesion on an MRI scan within the last 12 months
- Or presence of new or enlarging T2 lesions within the last 12 months

A combination of clinical and/or imaging findings is also accepted for inclusion.

Protocol No. COMB157G23101

The primary outcome will be to demonstrate the treatment effectiveness of ofatumumab in subjects with relapsing forms of MS as measured by ARR at 96 weeks. This Phase IIIb study will provide additional data on patient reported outcomes, biomarker outcomes and explore the utility of digital tools for patient assessments and treatment persistence / adherence.

Exploratory outcomes include assessments of processing speed, daily activity, physical functioning, and patient reported outcomes. Outcomes will be captured digitally and compared to clinical assessments wherever possible. NfL and CCI monitoring during the trial will better elucidate the underlying disease activity during RMS.

2 Objectives and endpoints

Table 2-1 Objectives and related endpoints

Objective(s)	Endpoint(s)		
Primary objective(s)	Endpoint(s) for primary objective(s)		
Demonstrate the effectiveness of ofatumumab 20 mg s.c. administered every 4 weeks in subjects with relapsing forms of MS who had breakthrough disease on fumarates or fingolimod	Annual relapse rate (ARR, based on confirmed relapses) measured over the 96 weeks		
Secondary objective(s)	Endpoint(s) for secondary objective(s)		
 Evaluate the safety of ofatumumab 20 mg s.c. administrated every 4 weeks in subjects with relapsing forms of MS who had breakthrough 	 Proportion of subjects with adverse events, including injection related reactions Proportion of patients with laboratory or vital signs results meeting abnormal criteria 		
disease on fumarates or fingolimod	 The proportion of subjects discontinuing treatment due to insufficient effectiveness (lack of efficacy) or tolerability/safety reasons 		

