4.6 Rationale for public health emergency mitigation procedures

During a public health emergency as declared by local or regional authorities e.g., pandemic, epidemic, or natural disaster, mitigation procedures to ensure subject safety and trial integrity may be implemented. Notification of the public health emergency as declared by local or regional authorities should be discussed among investigators and Novartis. All procedures adapted to the situation must be submitted, if required as per local regulations, through a protocol amendment for approval by local or regional Health Authorities and Ethics Committees prior to implementation of mitigation procedures.

5 Population

The study population will consist of adult subjects with RMS fulfilling all the eligibility criteria listed below. The study is planned to be conducted in approximately 120-170 centers worldwide. It is aimed to enroll a total of approximately 555 subjects. Subjects who enroll and prematurely discontinue study will not be replaced.

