6.1.4 Treatment duration

The planned duration of treatment is 96 weeks. Subjects may be discontinued from treatment earlier as per criteria in Section 9.1.1.

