9.2.1 Safety Follow-up

Subjects moving into the Safety Follow-up period, as described in Section 3, will continue for 6 months post last dose of ofatumumab treatment. A shorter follow-up time is acceptable if subjects select a different MS treatment during this period as presented below.

At the EOS + M6 Visit:

- If a subject has IgG and IgM results ≥ screening or LLN, this visit shall be considered final clinic visit for the subject. The End of Safety Follow-up visit will be performed by telephone contact to inform the subject that his or her participation in Safety Follow-up has ended; the disposition form will be completed at that time and the AE and concomitant medications eCRF will be updated if necessary to record any new or worsening events or medication changes since the last clinic visit.
- If a subject has either IgG or IgM results < screening or LLN, Safety Follow-up clinic visits will continue on a plus 3 monthly basis until both IgG and IgM values are ≥ screening or LLN. The End of Safety Follow-up visit will be performed by telephone contact to inform the subject that his or her participation in Safety Follow-up has ended; the disposition form will be completed at that time and the AE and concomitant medications eCRFs will be updated if necessary to record any new or worsening events or medication changes since the last clinic visit; refer to Table 8-2.

• Note: All IgG and IgM results are required to be confirmed by a Central Laboratory result. IgG/IgM assessments performed by a local laboratory under the Public Health Emergency mitigation procedures defined in Section 8.4.5 are not to be used to determine if the subject has met the criterion for their last immunoglobulin follow-up visit. During a Public Health Emergency, subjects should continue to be monitored until it is feasible and safe to schedule a clinic visit to obtain a sample for central laboratory evaluation unless Last Subject Last Visit (LSLV) has already been declared for the study. In such circumstances, please follow the guidance presented below.

Patients starting a different MS treatment during Safety Follow-up:

• During Safety Follow-up subjects may receive any DMT for the treatment of MS as the investigator deems necessary. Prior to starting the MS DMT, subjects will be brought in for their final Safety Follow-up visit. This visit will be the End of Safety Follow-up visit for the subject and the disposition page will be completed at this time.

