10.1.4 Reporting MS relapse as a SAE

MS relapses are one of the effectiveness endpoints in this study; hence, they are exempt from SAE reporting although they may meet the SAE definition on the basis that they are considered medically significant and are frequently associated with hospitalization. These events will therefore be reported on the MS relapse eCRF instead of the SAE form. However, if, in the judgment of the Investigator, a MS relapse is unusually severe or medically unexpected and warrants specific notification, then an SAE form must be completed and submitted according to SAE reporting procedures outlined above.

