12.4.2 Statistical model, hypothesis, and method of analysis

The primary analysis will describe the test for null hypothesis (H0): ARR >=0.18 versus

alternative hypothesis (H1): ARR<0.18. The ARR will be estimated for the entire duration by a negative binomial model with log-link and subject's time in study (as natural log of time in years) will be used as an offset with number of relapses in previous year, baseline EDSS, baseline number of T1 Gd enhancing lesions and the patient's age at baseline, prior MS therapies (fumarates or fingolimod) as covariates. The list of covariates in the model can be modified based on convergence of the statistical model. In addition, ARR will be calculated as number of confirmed relapses divided by time in study in year will also be presented for the entire duration. The ARR will also be summarized by yearly interval starting from the first dose of ofatumumab.

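### Planned relapse follow-up after stopping drug falls short of the 96-week intent-to-treat ARR, and the minimum contact list omits MS relapse

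*Protocol*

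**What the plan says.** **The claim.** The protocol summary (Data analysis) states: "All efficacy data will be analyzed according to the intent-to-treat principle". Table 2-1 and SAP Table 1-1 give the primary endpoint: "Annual relapse rate (ARR, based on confirmed relapses) measured over the 96 weeks".

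**After stopping drug.** Protocol 9.1.1 and 9.2 send the subject to an End of Study visit as soon as possible and then to Safety Follow-up under Table 8-2. That table schedules MS relapse and EDSS at 3 and 6 months after End of Study, at any additional visits, and at the end visit for early discontinuation. Section 8.3 lists both as efficacy assessments under Tables 8-1 and 8-2.

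**How long.** Section 9.2.1 sets Safety Follow-up at 6 months after the last dose; it is prolonged only for low IgG or IgM. If the subject is to start another DMT, a final visit comes first: "This visit will be the End of Safety Follow-up visit for the subject and the disposition page will be completed at this time".

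**The minimum.** Section 9.1.1 adds: "After study drug discontinuation, at a minimum, in abbreviated visits, the following data should be collected at clinic visits or via telephone/email contact". Two items follow, new or concomitant treatments and AEs/SAEs.

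**Where relapses are recorded.** Section 10.1.4 keeps MS relapses off the SAE form unless unusually severe or unexpected: "These events will therefore be reported on the MS relapse eCRF instead of the SAE form". Section 8.3.1 says the same of AE reporting, asks for symptoms to be queried at remote contacts during the study, and makes confirmation depend on an EDSS rating.

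**The analysis.** SAP 2.5.1 counts confirmed relapses from first dose to the efficacy cutoff date and ends time in study on that date. The sentence in SAP 2.1 that should define the cutoff breaks off in the public text. SAP 2.5.3 to 2.5.5 and protocol 12.4.3 and 12.4.4 are wholly or largely redacted.

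**The concern.** An intent-to-treat ARR over 96 weeks needs relapses counted to Week 96 whether or not the subject stays on drug. The collection plan does not run that far for early stoppers. Three parts of the 96 weeks are thinly covered or not covered:

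- time reached only by abbreviated visit, telephone or email, where relapse is not a required item and a remote contact alone yields no EDSS to confirm one;
- time beyond about 6 months after the last dose;
- time after another DMT starts.

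The trial has one arm and tests against a fixed value, so no control group shares the loss. The assumed ARR of 0.16 lies only 0.02 below the null value of 0.18. If those who stop are those who are relapsing, the reported rate would describe a more favourable stretch of time than the intent-to-treat label suggests.

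**Working it through.** No stated figure is in dispute. The sample size ("It is aimed to enroll a total of approximately 555 subjects") cannot be reproduced, because power, dispersion and dropout are not readable.

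**Inputs from the documents.** Assumed on-drug ARR 0.16 (protocol 12.8). Null value from 12.4.2: "The primary analysis will describe the test for null hypothesis (H0): ARR >=0.18 versus" an ARR below that value. From 6.1.4: "The planned duration of treatment is 96 weeks", so T = 672/365.25 = 1.84 years.

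**Assumptions.** The unobserved share f of planned person-time, the share d of subjects who stop, and the relapse rate q after stopping. The documents give none of them.

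**Step 1: rate needed to reach 0.18.** Full 96-week ARR = (1 − f) × 0.16 + f × q. Setting this to 0.18 gives q = 0.16 + 0.02/f.

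- f = 5%: q = 0.56
- f = 10%: q = 0.36
- f = 15%: q = 0.29

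**Step 2: what f means in dropout.** Let stopping times be uniform over 96 weeks.

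- Mean off-drug time per stopper is T/2 = 0.92 years.
- With w = 0.5 years of follow-up, the mean covered time is [w(T − w) + w²/2]/T = 0.43 years.
- The uncovered share of off-drug time is 1 − 0.43/0.92 = 53%.
- If relapses are counted through Safety Follow-up, f = 0.53 × d/2 = 0.265d. Then f = 5%, 10% and 15% need d of about 19%, 38% and 57%.
- If counting ends when drug stops, f = d/2, and d is 10%, 20% and 30%.

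**Step 3: ARR under three counting rules, on-drug rate 0.16.** Full 96 weeks = (1 − d/2) × 0.16 + (d/2) × q. The middle column adds the 0.43 years per stopper to both events and time.

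| d | q | To stop of drug | Plus 6 months | Full 96 weeks |
|---|---|---|---|---|
| any | 0.16 | 0.160 | 0.160 | 0.160 |
| 10% | 0.32 | 0.160 | 0.164 | 0.168 |
| 20% | 0.32 | 0.160 | 0.168 | 0.176 |
| 10% | 0.50 | 0.160 | 0.168 | 0.177 |
| 20% | 0.50 | 0.160 | 0.177 | 0.194 |

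**Step 4: where the test sits.** With 555 subjects, full follow-up and a Wald bound on the log rate, variance (1/(ARR × T) + k)/555, the estimate must fall below about 0.158 (dispersion k = 0) to 0.153 (k = 2) for the one-sided 95% upper bound to clear 0.18. These k values are assumed. Steps 1 and 3 therefore show how far the estimated quantity moves; they do not show a reversed test.

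**Step 5: if the drug performs as in Phase 3.** With an on-drug rate of 0.10, d = 20% and q = 0.50, the full 96-week ARR is 0.9 × 0.10 + 0.1 × 0.50 = 0.14, still below 0.18.

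**The case against.** The best defence is that relapse collection continues after discontinuation. Table 8-2 schedules MS relapse and EDSS for those who attend. Section 8.3.1 tells subjects to report symptoms at once, arranges unscheduled visits and puts all relapses, confirmed or not, on the relapse form. The list in 9.1.1 is a floor. In a single-arm trial, intent-to-treat may mean no more than analysing everyone treated, which is how the FAS is defined. This stands, and it limits the gap to the three parts named above. It does not carry follow-up to Week 96 or put relapse on the minimum list.

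Three stronger readings are tempting, and the documents do not support them.

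- **The primary ARR is an on-treatment rate, biased toward success.** That depends on the efficacy cutoff, which cannot be read. The SAP change history shows that the cutoff was updated and a section on intercurrent events added, so the matter may be handled there and must not be called missing. The 6mCDW analysis (SAP 2.14.1) uses the end of the treatment epoch, but that is only indirect evidence for ARR. Because counts and time end on one date, truncation lowers the ARR only if the post-stop rate is higher, and no document figure shows that it is.
- **Sites have no prompt to ask about relapse.** Section 8.3.1 supplies one for remote contacts.
- **Section 9.1.1 contradicts itself** by discontinuing a subject from the study after 6mCDW and then saying that those who stop drug are not withdrawn. Section 9.1.2 separates withdrawal of consent from discontinuation, and both statements lead to Safety Follow-up.

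**Conclusion.** The point holds as a mismatch between the intent-to-treat label over 96 weeks and the planned collection of relapses after drug is stopped. Some post-stop relapses can go uncounted. The size is conditional: zero if subjects relapse at the same rate after stopping, and 0.008 to 0.034 on the ARR scale in Step 3 when counting ends at the stop of drug (10% to 20% stopping, post-stop rate 0.32 to 0.50). About half of that difference remains if Safety Follow-up is counted. It matters if the true ARR is near the assumed 0.16. With an on-drug rate of 0.10, the Step 5 scenario stays below 0.18.

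The correction is worth making however the cutoff is defined. If the cutoff includes Safety Follow-up, abbreviated contacts can add time at risk without relapse ascertainment, which lowers the ARR at any positive relapse rate. If it ends with the treatment epoch, the intent-to-treat wording overstates what is estimated.

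**What to change.** 1. Add MS relapse to the minimum list in protocol 9.1.1: onset date, with an unscheduled EDSS visit if the subject agrees, recorded on the MS relapse eCRF.
2. Reword the intent-to-treat sentence in the protocol summary: all treated subjects are analysed over observed study follow-up, which for those who discontinue does not extend to Week 96.
3. If the efficacy cutoff does not already include Safety Follow-up, report a supplementary ARR with confirmed relapses and time at risk through Safety Follow-up, to Week 96 at most.

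The cost is one item in a contact that already takes place, one sentence and at most one further model run. Items 2 and 3 need no new data. Two limits remain. A relapse reported by telephone without an EDSS stays unconfirmed and enters only the all-relapse sensitivity analysis (listed for SAP 2.5.5 in the change history). Time beyond Safety Follow-up stays unobserved.
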